2.3.2.2. Quality of Life Endpoint – SF-36v2

The SF-36v2 is a 36-item self-report instrument that measures generic health-related quality of life in 8 specific dimensions plus 1 additional question that asks respondents to rate the amount of change experienced in their health in general (Maruish, 2011). It allows for the scoring of 2 component summary indices: the Physical Component Summary (PCS) score and the Mental Component Summary (MCS) score. The SF-36v2 is scored as 8 subscales representing separate domains of functional health and well-being:

- Physical Functioning (PF: 10 questions, # 3a to 3j)
- Role-Physical (RP; role limitations due to physical problems: 4 questions, # 4a to 4d)
- Bodily Pain (BP: 2 questions, # 7 to 8)
- General Health Perceptions (GH: 5 questions, # 1, 11a to 11d)
- Vitality (VT: 4 questions, # 9a, 9e, 9g, and 9i)
- Social Functioning (SF: 2 questions, # 6 and 10)
- Role-Emotional (RE; role limitations due to emotional problems: 3 questions, # 5a to 5c)
- Mental Health (MH: 5 questions, # 9b to 9d, 9f, 9h)

Responses to items allow for direct calculation of subscales for each of the 8 dimensions, while PCS and MCS scores are computed from weighted subscale scores (Maruish, 2011). The lower the score the more disability, the higher the score the less disability. A score of 50 is the mean in the US General Population. The standard deviation is 10 for all scales and both summary measures. The SF-36v2 will be scored using the algorithm provided by Optum with the instrument license (Health Outcomes™ Scoring Software 4.5). Algorithms that allow for the evaluation of summary component scores in the presence of missing data have been developed using Item Response Theory (IRT) and regression methods. Scores for respondents with

incomplete answers can be derived using the maximum data recovery approach for the missing data estimation for all scales except the PF scale. For the PF scale, an estimated score based on an IRT model is utilized as long as at least one of its items has valid data, otherwise the scale score will be missing. Both the PCS score and the MCS score can be calculated if (1) at least seven scale scores are available, (2) the PF scale is not missing when evaluating the PCS, and (3) the MH scale is not missing when calculating the MCS. The scoring algorithm to apply to the calculation of the summary scores depends upon which particular scale score is missing from the 8-scale profile.

- Change and percent change from PRONTO and OLE baselines in SF-36v2 PCS to each visit

2.3.2.3. Functional Endpoint - 6MWT Distance

The 6MWT is a practical simple test that requires a minimum walking length of 25 m but no exercise equipment or advanced training for technicians. The walking track or area should be the same for all tests for a subject. This test measures the distance that a subject can quickly walk on a flat, hard surface in a period of 6 minutes.

- Change and percent change from PRONTO and OLE baselines in the 6MWT distance (meters) to each visit

2.3.2.4. Renal Endpoints

The following endpoints will be evaluated in the Renal Evaluable Population (see Section 5).

For these subjects, renal response categories (modified from [Palladini, 2014](#) ; [Appendix 2](#)) are defined as:

Response	Stable	Progression
≥ 30% decrease from baseline or < 0.5g/24 hours post-baseline result of proteinuria (measured by 24-hour urine total protein excretion) in the absence of renal progression	Assessment was neither Response nor Progression	≥ 25% decrease in eGFR from baseline Note: if assessment qualifies as both Response and Progression, then assessments will be counted as progression

Best response is defined as the most favorable category (response, stable, or progression) across all visits. Subjects will be classified as responders or non-responders. Non-response is defined as either stable or progression.

- Renal best response from PRONTO and OLE baselines (see Section 2.2.4). Best response will be evaluated over the course of the study
- Renal response from PRONTO and OLE baselines (see Section 2.2.4) at each visit
- Change and percent change from PRONTO and OLE baselines (see Section 2.2.4) to each visit in creatinine, proteinuria, and estimated glomerular filtration rate (eGFR)

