2.2.4.2. OLE Baseline

The OLE Baseline for the 6MWT will use the PRONTO Baseline for 6MWT. Otherwise, OLE Baseline is defined as the last assessment prior to first infusion in the OLE.

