5. ANALYSIS POPULATIONS

The NEOD001 Safety Population will include all subjects who received any amount of NEOD001 in the original parent study (NEOD001-201).

The OLE Safety Population will include all subjects who received any amount of NEOD001 in the OLE study.

The Renal Evaluable Population will include subjects who were in the Renal Evaluable Population in the original parent study (NEOD001-201), defined as subjects who had proteinuria >0.5g/24 hours (measured by 24-hour urine total protein excretion), at baseline and at least one post-baseline assessment of proteinuria in NEOD001-201.

The Peripheral Neuropathy Evaluable Population will include subjects who were in the in the Peripheral Neuropathy Evaluable Population in the original parent study (NEOD001-201), defined as subjects who had ascending sensorimotor neuropathy due to AL amyloidosis etiologies at screening, had a baseline Neuropathy Impairment Score–Lower Limbs (NIS-LL) total score of 2 or greater and at least one post-baseline NIS-LL total score in NEOD001-201.

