8. EFFICACY ANALYSES

All recorded efficacy endpoint data will be presented in by-subject data listings for the OLE Safety Population.

Analyses will be produced in both NEOD001 Safety Population and OLE Safety Population, unless otherwise specified. Data, visit window, and treatment group to be used for each population as below:

1. NEOD001 Safety Population:
 - Data: Pooled data from parent and OLE study
 - Visit window: PRONTO visit window for data in parent study, OLE therapy visit window for OLE data with exclusion of OLE Baseline.
 - Treatment: Placebo and NEOD001 subjects received in NEOD001-201 study and Overall
2. OLE Safety Population:
 - Using data from OLE study only
 - Visit window: OLE therapy visit window
 - Treatment: NEOD001

Analyses in Renal Evaluable Population or Peripheral Neuropathy Evaluable Population will be presented in the same manner described above for NEOD001 Safety Population and OLE Safety Population.

Baseline in all efficacy analyses refers to PRONTO Baseline and OLE Baseline, unless otherwise specified.

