APPENDIX 2. ORGAN RESPONSE AND PROGRESSION CRITERIA

Organ	Response	Progression
Heart/Cardiac ^{a,b}	NT-proBNP response (>30% and >300 ng/L decrease in subjects with baseline NT-proBNP \geq 650 ng/L) OR NYHA class response (\geq 2 class decrease in subjects with baseline NYHA class III or IV) ^b	NT-proBNP progression (>30% and >300 ng/L increase) ^c
Renal ^d	\geq 30% decrease in proteinuria or drop of proteinuria below 0.5 g/24 hours in the absence of renal progression	\geq 25% decrease in eGFR
Peripheral Nerve ^e	NIS-LL increase from baseline of <2 points	NIS-LL increase from baseline of \geq 2 points

Abbreviations: ALP = alkaline phosphatase; eGFR = estimated glomerular filtration rate; NIS-LL = Neuropathy Impairment Score–Lower Limbs; NT-proBNP = N-terminal pro brain natriuretic peptide; NYHA = New York Heart Association.

a Modified from Table 2 in [Comenzo 2012](#).

b NYHA class not considered for primary efficacy endpoint analyses.

c Subjects with progressively worsening renal function cannot be scored for NT-proBNP progression.

d [Palladini 2014](#).

e [Coelho 2012](#).

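### Renal response from OLE Baseline: a subject already below 0.5 g/24 h there is scored Response, absent renal progression, with unchanged or rising proteinuria, although SAP Appendix 2 and protocol Appendix 3 require a drop below 0.5

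*SAP*

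**What the plan says.** SAP 2.3.2.4 gives two routes to renal Response. One is a decrease in proteinuria of at least 30% from baseline. The other is a "< 0.5g/24 hours post-baseline result of proteinuria (measured by 24-hour urine total protein excretion) in the absence of renal progression". Renal progression is an eGFR decrease of at least 25%, and a note makes progression prevail when both apply.

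The section requests "Renal response from PRONTO and OLE baselines (see Section 2.2.4) at each visit", and best response from the same two baselines. SAP 8 confirms the general rule: "Baseline in all efficacy analyses refers to PRONTO Baseline and OLE Baseline, unless otherwise specified". SAP 8.9.1 and 8.9.2 specify nothing different for the renal endpoints.

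Under SAP 2.2.4.2, for everything except the 6-minute walk, "OLE Baseline is defined as the last assessment prior to first infusion in the OLE". No minimum proteinuria is set there. Under SAP 5 the Renal Evaluable Population consists of subjects "who were in the Renal Evaluable Population in the original parent study (NEOD001-201), defined as subjects who had proteinuria >0.5g/24 hours" at the parent-study baseline, with at least one later proteinuria value in that study. The threshold is not applied again at OLE entry.

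SAP Appendix 2 words the criterion as a 30% or greater "decrease in proteinuria or drop of proteinuria below 0.5 g/24 hours in the absence of renal progression". Protocol Appendix 3 has the same wording.

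**The concern.** The below-0.5 route looks only at where the subject is after baseline, not at where the subject started. From PRONTO Baseline this makes no difference, because every evaluable subject starts above 0.5. From OLE Baseline it does: a subject whose proteinuria fell below 0.5 g/24 h during the parent study stays in the Renal Evaluable Population and then qualifies as a responder to OLE treatment without any further improvement.

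Best response takes the most favorable category over all visits, so a single value below 0.5 without progression is enough.

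At stake is the meaning of two rates that the SAP kept and reports with exact 95% confidence intervals: renal best response and renal response by visit, both from OLE Baseline. A reader will take response from OLE Baseline to mean improvement during the extension. For these subjects it may mean no change, or a rise that stays under the threshold.

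**Working it through.** The plan gives no figure to reproduce on this point, so the check applies the two wordings to the same data.

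**Rules**

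- SAP 2.3.2.4: Response if (decrease ≥30% or post-baseline <0.5) and the eGFR decrease is <25%.
- Appendix wording, reading a drop below 0.5 as starting at 0.5 or more and ending below it: Response if (decrease ≥30%, or baseline ≥0.5 and post-baseline <0.5) and the eGFR decrease is <25%.
- Both: Progression if the eGFR decrease is ≥25%; otherwise Stable.

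**Hypothetical pairs** (proteinuria in g/24 h)

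| Baseline → post | Change | eGFR | SAP 2.3.2.4 | Appendix wording |
|---|---|---|---|---|
| 0.30 → 0.30 | 0% | 60 → 60 | Response | Stable |
| 0.30 → 0.45 | +50% | 60 → 60 | Response | Stable |
| 0.10 → 0.49 | +390% | 60 → 60 | Response | Stable |
| 0.40 → 0.39 | −2.5% | 60 → 60 | Response | Stable |
| 0.30 → 0.45 | +50% | 60 → 44 (−26.7%) | Progression | Progression |
| 0.60 → 0.45 | −25% | 60 → 60 | Response | Response |
| 2.0 → 1.3 | −35% | 60 → 60 | Response | Response |

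**Where the rules differ.** With eGFR stable, on a grid of 0.01 g/24 h with baseline 0.51 to 9.99 and post-baseline 0.01 to 9.99, they never differ. The PRONTO-baseline analysis is therefore untouched. With both values below 0.5 they differ in 1,566 of 2,401 grid pairs; that counts grid cells, not subjects.

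**Direction and size.** Let f be the share of subjects in the denominator who are below 0.5 at OLE Baseline, s the share of those scored Response under SAP 2.3.2.4, d the share of those with a decrease of at least 30% and no progression, and r the response rate in everyone else, which is the same under both rules.

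- SAP rate = (1 − f)r + fs
- Appendix rate = (1 − f)r + fd
- Difference = f(s − d)

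For a baseline below 0.5, a 30% decrease ends below 0.7 × 0.5 = 0.35, so everyone counted in d is also counted in s. Hence d ≤ s and the difference cannot be negative. Affected subjects move from Response to Stable in the three-category table; Progression counts do not change.

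None of f, s and d is in the documents. For scale only, assume f = 10%, 20% or 30%, s = 100%, d = 0 and r = 20%. The rates are then 28% against 18%, 36% against 16%, and 44% against 14%. The gap equals the assumed f, so this restates the input. With s = 75% and d = 20%, f = 10% gives 0.10 × 0.55 = 5.5 points and f = 30% gives 0.30 × 0.55 = 16.5 points. For by-visit rates, f is the share among subjects observed at that visit, because SAP 8.2.2 uses observed cases there.

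**The case against.** The strongest reply is that the wording is deliberate. SAP 2.3.2.4 introduces its table with "For these subjects, renal response categories (modified from" and a published source, and the conflict turns on one word in the appendices, which state no numerical starting value. The wording may well be deliberate. But the same sentence points to SAP Appendix 2, which keeps the drop, and nowhere does the SAP say or justify that the condition was removed. If maintained low proteinuria is meant to count, the SAP should say so and show it separately from new response.

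The second reply is that little depends on it. That stands. There is no sample-size basis, no multiplicity control and no decision rule. Change and percent change in proteinuria are reported from both baselines, and by-subject listings would show a subject who went from below 0.5 to below 0.5.

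Some stronger readings are tempting but unsupported:

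- A reader might infer that deteriorating kidneys are scored as response. An eGFR decrease of at least 25% overrides Response, and a rise that reaches 0.5 g/24 h or more does not qualify.
- A reader might take the silence of SAP 10 on the renal criterion as proof of an undeclared change. That section lists analyses removed when the program was discontinued; it is not a log of wording changes to retained criteria.
- A reader might infer that the inflation is large. The documents give no count of subjects below 0.5 at OLE Baseline. For best response, one visit with a 30% decrease and no progression makes the subject a responder under both rules, which narrows the gap.

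**Conclusion.** The point holds for the OLE-baseline renal response rates only. As written, SAP 2.3.2.4 classifies unchanged or rising proteinuria as Response for a subject already below 0.5 g/24 h at OLE Baseline, provided the value stays below 0.5 and there is no renal progression. That conflicts with SAP Appendix 2 and protocol Appendix 3.

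The direction is certain: the rates can only be too high. The excess is the share of the denominator made up of subjects below 0.5 at OLE Baseline who score Response without a 30% decrease. That share cannot be found from the documents, and it is zero if no such subject exists. The conclusion assumes the ordinary reading of a drop below 0.5, namely starting at or above it.

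Because the endpoint is descriptive, the consequence is a misleading rate, not a wrong decision. It is still worth correcting, since the remedy is one condition.

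**What to change.** In the Response cell of SAP 2.3.2.4, let the below-0.5 route count only when proteinuria at the reference baseline was at least 0.5 g/24 h. Keep the 30% decrease route for everyone. Beside the OLE-baseline best-response and by-visit rates, report the number of subjects already below 0.5 g/24 h at OLE Baseline.

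Restricting the OLE-baseline analysis to subjects above 0.5 at OLE Baseline would also remove the conflict, but it changes the denominator and gives a different rate. The condition above leaves the Renal Evaluable Population as defined.

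A separate, minor clarification is worth making at the same time. Protocol Table 1 and section 6.1.1.1 list no 24-hour urine at OLE Screening for subjects less than 60 days from their last PRONTO visit; it is listed only for those at 60 days or more. SAP 2.2.4.2 does not restrict OLE Baseline to samples collected in the extension, but SAP 8 describes the OLE analyses as "Using data from OLE study only". One sentence should state that OLE Baseline proteinuria may be the last PRONTO 24-hour urine.

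The cost is SAP wording and one count in the OLE-baseline renal tables. No new data are needed, and the denominator does not change.

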2.3.2.5. Peripheral Neuropathy Endpoint - NIS-LL Total Score

- Change and percent change from PRONTO and OLE baselines (see Section 2.2.4) to each visit in NIS-LL total score will be evaluated in the Peripheral Neuropathy Evaluable Population (see Section 5).

2.3.2.6. Time to All-Cause Mortality (Overall Survival)

Any deaths after the first infusion of study drug (i.e. study day 1) through the study's last subject last visit (LSLV). Time (months) to event will be calculated as: (date of death - the date of first study drug infusion + 1) / 30.4375. Subjects will be censored at their last assessment known to be alive prior to LSLV.

2.3.2.7. Other Efficacy Data

Below are the other efficacy data collected in NEOD001-OLE251 study:

- Visual Analog Scale – Pain Intensity (VASPI)
- Kansas City Cardiomyopathy Questionnaire (KCCQ)
- Eastern Cooperative Oncology Group (ECOG) performance
- Free light chains (sFLCs), serum and 24-hour urine protein electrophoresis (PEP), and serum and urine immunofixation electrophoresis (IFE)
- Severity of disease-related symptoms including any changes from baseline
- Pharmacokinetics (PK)

3. SAMPLE SIZE JUSTIFICATION

Not applicable as this is an extension study for subjects who completed Study NEOD001-201.

4. GENERAL STATISTICAL METHODS

4.1. Reporting Conventions

Individual subject data obtained from electronic case report forms (eCRFs), central laboratories, external sources, and any derived data will be presented in data listings by subject. The primary data source will be used for all analyses. All data listings that contain an evaluation date will contain a relative study day. Pre-treatment and on-treatment study days are numbered relative to the day of the first dose of study drug in the OLE which is designated as Day 1. The preceding day is Day -1, the day before that is Day -2, etc.

All output will be incorporated into Microsoft Word rich text format (.rtf) files, sorted and labeled according to the International Council for Harmonisation (ICH) recommendations, and formatted to the appropriate page size(s).

For categorical variables, summary tabulations of the number and percentage of subjects within each category (with a category for missing data) of the parameter will be presented. Percentage calculations will be based on non-missing data, unless otherwise specified. Percentages are rounded to 1 decimal place, unless otherwise specified.

For frequency counts of categorical variables, categories whose counts are zero will be displayed for the sake of completeness. For example, if none of the subjects discontinued due to “lost to follow-up,” this reason will be included in the table with a count of 0. Percentages based on frequency counts will be presented to one decimal place, and values less than 1% will be presented as “<1%.” Values less than 100% but greater than 99% will be presented as “>99%.”

For continuous variables, the number of subjects, mean, standard deviation (SD), median, 25th quartile (Q1), 75th quartile (Q3), minimum, and maximum values will be presented. The precision of summary statistics, unless otherwise specified will be as follows: mean and median to 1 more decimal place than the raw data, and SD to 2 decimal places more than the raw data. In general, the number of decimal places should not exceed 3 decimal places unless appropriate. Confidence intervals (CIs) will be provided and will be rounded to 1 decimal place, unless otherwise specified, in the table and listing shell.

For tables where rounding is required, rounding will be done to the nearest round-off unit. For example, when rounding to the nearest integer, values $\geq XX.5$ will be rounded up to $XX+1$ (e.g., 97.5 will round up to 98), while values $<XX.5$ will be rounded down to XX (e.g., 97.4 will round down to 97).

4.2. Computing Environment

All descriptive statistical analyses will be performed using SAS statistical software Version 9.4 or higher, unless otherwise noted. Medical history and AEs will be coded using Medical Dictionary for Regulatory Activities (MedDRA) version 19.0. Concomitant medications will be coded using World Health Organization (WHO) Drug Dictionary, B2 Enhanced September 2015.

4.3. Partial Dates and Unknown Times

If only a partial date is available and is required for calculation, the following standards will be applied:

- Death Date
 - The last date that each subject was known to be alive will be identified as the greatest date associated with the subject's completed assessments, including telephone contacts at which the subject was confirmed to be alive.
 - For missing day only – Day will be imputed as the first day of the month (i.e., 1) with the following exception: if the partial date falls in the same month as the last known alive date, then the partial date will be imputed to equal the last known alive date.
 - For missing day and month – Day and month will be imputed as the first day of the year (i.e., 1 January) with the following exception: if the partial date falls in the same year as the last known alive date, then the partial date will be imputed to equal the last known alive date.
- Start Dates (e.g., event date, AE onset date, start date of medication, or hospitalization admission date)
 - For missing start day only – Day will be imputed as the first day of the month (i.e., 1) with the following exception: if the partial date falls in the same month and year as the date being used in the calculation (e.g., first infusion date, informed consent date), then the partial date will be imputed to equal the date being used for the calculation.
 - For missing start day and month – Day and month will be imputed as the first day of the year (i.e., 1 January) with the following exception: if the partial date falls in the same year as the date being used in the calculation (e.g., first infusion date, informed consent date), then the partial date will be imputed to equal the date being used for the calculation.
 - When applicable, imputed start dates must be prior to the stop date.
- Stop Dates (e.g., AE resolution date or stop date of medication)
 - For missing stop day only – Day will be imputed as the last day of the month (i.e., 28, 29, 30, or 31).
 - For missing stop day and month – Day and month will be imputed as the last day of the year (i.e., 31 December).
 - Imputed stop dates must be on or after the start date.

All data recorded on the case report form will be included in data listings that will accompany the CSR.

4.4. Data Conventions

The precision of original measurements will be maintained in summaries, when possible.

Quantitative laboratory tests containing less than (<) and greater than (>) symbols are test results that are below and above quantifiable limits, respectively. In order to retain these values for analysis purpose, the numeric portion of the result will be imputed and stored within the analysis datasets.

4.5. Standard Calculations

Variables requiring calculation will be derived using the following formulas:

- Days – A duration expressed in days between one date (*date1*) and another later date (*date2*) will be calculated using the following formulas:
duration in days = $date2 - date1 + 1$, where $date1 \geq \text{first infusion date}$
duration in days = $date2 - date1$, where $date1 < \text{first infusion date}$
- Months – A duration expressed in months is calculated as the number of days divided by 30.4375
- Years – A duration expressed in years between one date (*date1*) and another date (*date2*) is calculated using the following formulas:
duration in years = $(date2 - date1 + 1) / 365.25$, where $date1 \geq \text{first infusion date}$
duration in years = $(date2 - date1) / 365.25$, where $date1 < \text{first infusion date}$
- Age – Age is calculated as the number of years from the date of birth (*DOB*) to the specified date, e.g., date of informed consent (*DOIC*).
age (years) = $(DOIC - DOB + 1) / 365.25$
- Height – Height entries made in inches (in) are converted to centimeters (cm) using the following formula:
height (cm) = height (in) \times 2.54
- Weight – Weight entries made in pounds (lb) are converted to kilograms (kg) using the following formula:
weight (kg) = weight (lb) / 2.205
- Temperature – Temperature entries in degrees Fahrenheit are converted to degrees Celsius using the following formula:
temp (degrees Celsius) = $5 / 9 \times (\text{temp [degrees Fahrenheit]} - 32)$
- Body Mass Index (BMI) – BMI is calculated using height (cm) and weight (kg) using the following formula:
BMI (kg/m²) = weight (kg) / ([height (cm)/100]²)
- Change from baseline – Change from baseline will be calculated as:
Change = post baseline value – baseline value

- Percent change from baseline – Change from baseline will be calculated as:

$$\text{Percent change from baseline} = \left(\frac{[\text{post baseline value} - \text{baseline value}]}{\text{baseline value}} \right) \times 100$$

